## 6.0 Setting

The data for this study will be recorded in the operating room at MUSC. Coded and identifiable data will be stored electronically on a secure server in separate folders. Signed consent forms will be located in a locked cabinet in a locked laboratory in the Clinical Sciences Building at MUSC.

## 7.0 Recruitment Methods

An eligibility screening checklist will be used prior to completing the informed consent process. The screening will not require access to PHI and will be allowed under a waiver of signed consent for the prescreening. The screening checklist will contain only the inclusion and exclusion criteria for the study. The purpose of the screening is to ensure that patients meet ALL inclusion and exclusion criteria for the study prior to executing the informed consent. This process will work in the following manner: During a preoperative clinic visit with the PI, the PI will

ask the patient if they would like to learn more about the study. If so, the PI will then complete the screening checklist then sign and date the form. If the subject meets all inclusion and exclusion criteria, the PI will review the protocol and consent form with the patient and then leave the room in order to give the patient sufficient time to read the consent form.

The PI is the surgeon performing the surgery, so he will have the knowledge to carefully explain the research study. Careful attention will be placed on good communication. The PI will be sure to emphasize that participation in the study is not necessary for the standard of care surgery. He will also emphasize that the patient can withdraw from the study at any time prior to the surgery.

## **8.0 Consent Process**

Once the patient has been given an opportunity to review the consent form in detail, the PI, along with another member of the IRB-approved personnel team for this study, will re-enter the room and go over the sections of the consent with the participant. They will answer any questions the patient may have. The voluntary nature of the study will again be emphasized. It will also be emphasized that the patient may exercise their right to take the consent form home to discuss with family and friends prior to signing. For patients that provide consent to the research study during their clinic visit, a copy of the signed and dated consent form will be provided to them before leaving the clinic. The PI will also review the HIPAA authorization form prior to the patient signing the form. The patient will be given a copy of this form. Original forms will be placed in a locked cabinet in a locked laboratory in the Clinical Sciences Building at MUSC. On the morning of surgery, IRB-approved study personnel will once again review the study procedures and study consent document – emphasizing the voluntary nature of the study and the ability of the patient to withdraw at any time. Patients who did not sign the consent and HIPAA authorization forms during their clinic visit and who still wish to participate in the study will be able to sign the forms on the morning of surgery, at which time a copy of the signed and dated forms will be provided to them.

Patients will be informed during the consent process that information about them (including identifiable private information) may have all of their identifiers removed and used for future research studies or distributed to other researchers for future research without additional informed consent from them.

## **9.0 Study Design / Methods**

The study will begin with a medical chart review by the research staff, who will extract data elements from the patient's electronic medical record (EMR) to be stored in a database (see Data Management section).

Following this, the study will implement the steps described below (see Figure 1):

### **Step 1: Insertion of sECoG electrode**

After the burr hole is made as part of the clinical DBS procedure, we will insert an ECoG electrode in the subdural space to cover primary motor cortex for research purposes. The flat, circular, platinum-iridium contacts within the ECoG strip are arranged in 1 row of 6 contacts separated by 1 cm center-to-center and suspended in a silastic finish. The ECoG electrode is 75 mm x 8 mm in dimensions and each contact is 4 mm in diameter with a 2.3 mm exposed

surface. These electrodes come prepackaged sterilely and will be handled using standard operating room procedures. The sECoG electrode is anchored by a cable that will extend outside the burr hole and connect to an amplifier (Cascade Pro, Cadwell, Kennewick, WA). ECoG data will be amplified one thousand times and sampled on all 6 channels at 3000 Hz with each channel recorded in monopolar configuration referenced to a grounding needle in the scalp. sECoG recording will last a total of approximately 20 minutes, after which the sECoG electrode will be removed. sECoG recording will be manually switched on and off by IRB-approved study personnel in the operating room to assist with the procedure.

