#### **Procedure steps**

In brief, standard of care DBS surgery involves drilling a 1.4 cm burr hole in the skull and implanting an electrode that penetrates the brain parenchyma into the basal ganglia or thalamus. For patients participating in this research, all surgical procedures will be the same, with the exception of the research-dedicated steps: 1) the sECoG electrode will be inserted using the same burr hole drilled previously but will remain on the surface of the brain and will not penetrate the brain, 2) the tDCS electrodes will be applied to the scalp (awake patients with frameless DBS will also be outfitted with virtual reality goggles), 3) the tDCS electrodes will be activated (awake, frameless DBS patients will perform up to two motor tasks before, during and/or after stimulation and videotaped during the task); the task will not be performed if the patient is awake but has a stereotactic headframe on or is asleep under general anesthesia, 4) in all patients the surgical site will be photographed to capture the tDCS montage as well as any other aspect of the setup relevant to offline reconstruction of behavioral and physiology data), 5)

all research-related equipment will be removed from the surgical field, 6) the subject will proceed to have the DBS surgery as per standard of care.

DBS surgery is reimbursed by insurers using a Diagnosis Related Group (DRG) model. This means that once a patient is preauthorized by an insurer to undergo DBS surgery, the surgery, hospital stay and all related procedures are bundled together and covered at a fixed cost. Costs related to research activity during this study (20 minutes total) will be charged to a research account and will not result in additional charges to the patient, hospital or the patient's insurer. In a recently published study documenting 200 cases of sECoG insertion during DBS surgery in movement disorder patients and in which all study related procedures took place in 20 minutes or less ('Intraoperative electrocorticography for physiological research in movement disorders: principles and experience in 200 cases', by Panov et al, 2017), **no infections related to the sECoG electrode occurred**. In this study, we will allow 20 minutes total to include setup and breakdown of the study-related equipment.

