#### **Step 4: Fluoroscopy**

At the conclusion of the recording, several fluoroscopic images will be taken to capture the position of the tDCS and sECoG electrodes in situ. Fluoroscopy is already used in the standard of care DBS procedure to verify placement of the DBS lead. Finally, the tDCS electrodes, sECoG electrode and VR goggles will be removed.

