### **sECoG**

Insertion of electrodes onto the brain surface may precipitate bleeding from a ruptured blood vessel, damage to nearby structures, and increased risk of infection due to foreign body. These risks were outlined in a recent study (Panov et al, 2017) documenting 200 cases of sECoG insertion during DBS surgery in which all study related procedures took place in 20 minutes or less. In this study, 2 sECoG electrodes were unable to be inserted due to resistance and 8 others were associated with some complication, none of which were directly related to sECoG placement. The overall complication rate (again unrelated directly to sECoG insertion) was 5% (which is equivalent to the overall complication rate of DBS surgery without sECoG insertion) and **no infections related to the sECoG electrode occurred.** Nevertheless, to mitigate the risk of infection associated with sECoG placement, we will limit the total time dedicated to this study to 20 minutes. These electrodes come prepackaged sterilely and will be handled using standard operating room sterile procedure. Moreover, large cortical veins noted on preoperative imaging during surgical planning and/or any resistance detected during insertion will trigger immediate removal of the electrode, withdrawal of the patient from the study, and continuation with the DBS procedure.

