### **VR goggles**

Immersion in a virtual environment using a head mounted display has been associated with potential discomfort and health risks. In most cases, health implications are minor and consist of mostly temporary discomfort. Several studies have associated stereoscopic 3D viewing with eyestrain, visual discomfort and fatigue. However, Pölönen et al. concluded that viewing 3D environments for up to 2 hours is a relatively comfortable experience across all age levels, with short breaks reducing the risk of eyestrain and changes in visual function. The Samsung Gear VR, which shares many characteristics with the Oculus Rift headset used in this project, was successfully used over a prolonged time in an inpatient setting with no severe adverse events. However, patients often described the headset as uncomfortable and difficult to focus. To mitigate this risk, subjects in this study will wear the VR goggles for no more than 20 minutes. Awake, frameless DBS subjects will be instructed to notify a member of the IRB-approved

research team present in the operating room if they experience eyestrain, visual discomfort, discomfort associated with the headset and/or difficulty focusing. If awake, frameless DBS subjects report of any of these symptoms, the headset and electrodes will be removed and the standard of care DBS procedure will continue. Any data acquired will be retained for analysis.

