### **Fluoroscopy**

In addition to the fluoroscopy images that will occur as part of clinical care for the placement of the DBS electrode, there may be additional fluoroscopy images that occur to evaluate the placement of the research electrodes. Effective radiation dose is measured in milliSieverts (mSv). Background radiation exposure from the environment (e.g., cosmic rays from space) is approximately 6 mSv per year. Each fluoroscopic image is approximately 5 microSieverts ( $\mu$ Sv). According to the US Department of Energy, up to 50 mSV are allowed per year in adult radiology workers. Beyond this limit, additional radiation carries an increased risk of cancer. To mitigate this risk, the fluoroscopy will be administered by a certified radiation technologist who will use the lowest dose necessary for the image. Also, if the research electrode placement is captured in one of the fluoroscopic images taken as part of clinical care for the placement of the DBS electrode, no additional fluoroscopic images for research will be required.

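### Step 1 gives sECoG recording about 20 minutes, leaving little or no room under the 20-minute cap on all research time, and does not say that the cap governs

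*Combined protocol and SAP*

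**What the plan says.** All references are to the combined protocol and SAP.

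- **Recording time.** Section 9.0, Step 1: "sECoG recording will last a total of approximately 20 minutes, after which the sECoG electrode will be removed". The same step says that study personnel switch the recording on and off by hand.
- **Cap on research time.** Section 3.0, Procedure steps: "In this study, we will allow 20 minutes total to include setup and breakdown of the study-related equipment". That section lists insertion of the strip, application of the tDCS electrodes and removal of the research equipment among the research steps.
- **Purpose of the cap.** Section 13.0, sECoG: "to mitigate the risk of infection associated with sECoG placement, we will limit the total time dedicated to this study to 20 minutes". This follows a description of a 200-case series in which study procedures stayed within 20 minutes and no infection was attributed to the strip.
- **After recording.** Section 9.0, Step 4: "At the conclusion of the recording, several fluoroscopic images will be taken to capture the position of the tDCS and sECoG electrodes in situ", and then "Finally, the tDCS electrodes, sECoG electrode and VR goggles will be removed". Section 13.0, Fluoroscopy, adds that if a clinical image already shows the research electrodes, "no additional fluoroscopic images for research will be required".
- **Goggles.** Section 13.0, VR goggles, sets a separate ceiling: "subjects in this study will wear the VR goggles for no more than 20 minutes".

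**The concern.** The same figure, 20 minutes, is attached to two different quantities. In Sections 3.0 and 13.0 it is the whole research session. In Step 1 it is the recording, with removal of the strip placed after it. Insertion, recording and removal follow one another, so a recording that takes about the whole allowance leaves almost nothing for the other two.

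The limit is one the protocol sets for itself to protect patients. The strip is a research device in the subdural space, and Section 14.0 says no direct benefit to participants is expected. Step 1 is where personnel running the recording would look for its duration. A team could follow that step in good faith and go past the cap, because nothing there tells them which figure takes precedence.

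**Working it through.** This is a time budget. No sample-size or power formula is involved, and the plan offers no budget of its own to reproduce.

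**Inputs**

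- r = recording time: approximately 20 minutes (Section 9.0, Step 1).
- C = cap on all research time: 20 minutes (Section 3.0, Procedure steps; Section 13.0, sECoG).
- x = research time outside recording: insertion, removal, and any setup or fluoroscopy that does not overlap recording. The documents give no value, and none is assumed here.

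**Formula**

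Total T = r + x. The cap requires T ≤ C, so x ≤ 20 - r.

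**What must fall inside x**

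1. Insertion comes before recording, because nothing can be recorded until the strip is in place.
2. Removal comes after recording, by both Step 1 and Step 4.
3. tDCS and goggle setup could overlap recording. The documents do not say, so allow that all of it does.
4. Research fluoroscopy may need no extra time if a clinical image suffices. Allow that too.

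Even with the allowances in items 3 and 4, insertion and removal remain, so x > 0.

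**Numbers**

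- r = 20 exactly: x ≤ 20 - 20 = 0. Since x > 0, the total is 20 + x and the cap is passed by x minutes.
- r somewhat below 20, which the approximate wording permits. As an illustration, assume 17 to 19 minutes: x ≤ 20 - 19 = 1 minute, up to 20 - 17 = 3 minutes. Both statements hold if insertion and removal fit in that time.
- r somewhat above 20, which the approximate wording also permits: the cap has already been passed before removal begins.

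So the statements are compatible only when x is no larger than the amount by which recording falls short of 20 minutes. Neither quantity is given. Turned round, keeping the cap means r ≤ 20 - x.

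**The case against.** The strongest reply is that Step 1 is only describing the session. The protocol uses 20 minutes for the research activity charged to the research account, for the total with setup and breakdown, for the infection safeguard and for goggle wear, so Step 1 may be the same window loosely worded. It says approximately, sets no minimum, and the recording is under manual control, so staff can stop sooner. The cap itself is stated without qualification elsewhere.

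Much of this stands. The approximate wording means that a small non-zero insertion or removal time does not by itself break the cap, and loose wording is a plausible explanation. What remains is that the sentence names recording, places removal after it, and does not refer to the cap. No other section says that these 20 minutes include insertion and removal.

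Two stronger readings are tempting, and neither is supported:

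- **That the figures cannot both hold, or that patients face a known extra infection risk.** The first would need an exact 20 minutes. The second would need a value for x and a relation between added minutes and infection. The documents supply neither.
- **That Aim 1 or Aim 2 cannot be completed within the cap.** Section 3.0 says that "awake, frameless DBS patients will perform up to two motor tasks before, during and/or after stimulation". At the 3 minutes per run reported for the earlier study (Section 9.0, Step 3), two runs take 2 × 3 = 6 minutes, or 7 with one 1-minute rest. If Step 3 is read as allowing three runs, they take 3 × 3 = 9 minutes, or 11 with two rests. No tDCS duration is stated for either aim, so the documents do not show whether shorter recording would constrain them.

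**Conclusion.** The point holds as a minor correction to a stated safety limit. As written, Step 1 leaves little or no time within the 20-minute total for inserting and removing the strip, and it does not say that the total governs. The conclusion rests on two premises: that insertion and removal count as research time, which follows from the research steps listed in Section 3.0, and that neither can take place while recording is under way.

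The size of any overrun is x less whatever recording falls short of 20 minutes, and it cannot be determined from the documents. Nor can the added risk, if there is any. The design, sample size and analysis are unaffected.

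**What to change.** Keep the 20-minute total as the governing limit and reword the sentence in Section 9.0, Step 1. Suggested text: sECoG recording will stop early enough that insertion, recording, any research fluoroscopy and removal of all research equipment are completed within the 20-minute total research time. No fixed recording length need be stated. Logging the times of insertion and removal would let the study show that the limit was kept, but this is optional.

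The cost is one sentence of protocol text and somewhat less recording time than Step 1 now suggests, in both aims.

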## **Step 2: Placement of tDCS electrodes and virtual reality goggles**

We will place the tDCS electrodes onto the patient's scalp which will be previously shaved of all hair (depending on laterality of procedure – either unilateral or bilateral) in accordance with the standard clinical DBS procedure. The electrode array consists of one central electrode and four surrounding electrodes (total of five ring electrodes, each 1 cm in outer diameter, 2 mm thickness). The central electrode will be placed at a location directly overlying primary motor cortex as determined by coordinates generated through neuronavigational software used for DBS electrode trajectory planning. For purposes of sterility, the patient's scalp will be covered with an iodine-impregnated adhesive film per standard of care procedures. The electrodes, which will be sterilized with ethylene oxide prior to the procedure, will be secured in place using additional sheets of this film, which will serve as an additional preventive measure against possible infection. Next, the tDCS electrodes will be connected to a low-current generator placed away from the surgical field and powered by alkaline batteries. The device will be manually controlled by IRB-approved study personnel in the operating room to assist with the procedure. For presentation of visual images for patients who are awake and undergoing frameless DBS, patients will be outfitted with virtual reality goggles (Oculus Rift, Menlo Park, CA). The Oculus system also comes with a hand controller that is held by the patient and tracked in three-dimensional space, serving as a marker of upper extremity movement. Presentation of visual images will be manually controlled by IRB-approved study personnel in the operating room to assist with the procedure.

It is important to note that neither the tDCS nor sECoG electrodes will penetrate the brain at any time. Both electrodes will remain outside the brain itself. The tDCS electrode will remain on top of the scalp; the sECoG electrode will remain underneath the skull and on top of the brain surface (see Figure 1, Step 3). Only the DBS electrode performed for standard of care treatment of PD will penetrate the brain.

## **Step 3: Motor task for awake, frameless DBS patients**

After all electrodes and VR goggles have been set up, the goggles, which will be connected to a computer, will display an interactive task beginning with appearance of a red dot in the center of the screen for 3 seconds (Note that this task will be similar to the task used in the Rowland et al, 2015 study). This single red dot will be followed by a red and blue dot of the same size appearing together for a period of 3 seconds with the blue dot located 10 cm above the red dot. After 3 seconds, the red dot in the center of the screen will become green. When the blue dot located above the green dot is touched virtually (patient's outstretched finger approaches within 2 mm of the position of the dot), it will disappear and then reappear 10 cm below the green dot. When the blue dot is touched virtually at this location, it will reappear above the green dot again. Successive virtual touches will continue to cycle the blue dot a total of 5

[figure not shown]

Figure. 1. Recording and stimulation schematic. Following skin incision and burr hole drilling, an ECoG electrode is inserted into the burr hole over the cortical surface. The source electrode (anode) of the hd-tDCS electrode array is shown centered over primary motor cortex.

times. If no virtual touch is made at a location for 2 seconds, the blue dot will cycle to the next location automatically. Once the blue dot has cycled 5 times, both the blue and green dots will disappear and the red dot will reappear in the center of the screen (accompanied by an auditory cue) to complete 1 trial. Patients will be instructed to rest quietly when the red dot appears (rest phase). Appearance of the blue dot will signal that the patient is to prepare to move once the green dot appears (movement preparation phase). Patients will be instructed to move at a natural speed. This is to avoid confounding changes in beta and broadband gamma oscillations due to movement speed and force. Patients will be given an introduction to the task and an opportunity to practice several trials in the preoperative area while waiting for surgery to begin. Rest, movement preparation and movement execution will be analyzed as separate epochs. Beta and broadband gamma spectral power during each movement phase (rest, prep and move) will be analyzed separately. In our previous work (Rowland et al, 2015), the entire task took 3 minutes to complete. The entire task will be videotaped and repeated no more than twice. Videotaping will occur using a high-resolution web camera secured to a computer monitor facing the patient. The video signal is contemporaneous with all other data streams. Patients who are asleep will not perform the task or be videotaped.

All patients – whether awake or asleep – will undergo photography of the surgical site as well as any other aspect of the research necessary to reconstruct the electrode configurations (all patients) and/or behavioral task (awake, frameless DBS patients only).

